8.8 Flow chart for HOLDS trial

9 Outcome measures

9.1 Primary Outcome

• Caesarean Section (CS)

9.2 Secondary maternal outcomes

Clinical outcomes

- Epidural use during labour
- Duration of first, second and third stages of labour
- Time to birth from randomisation
- Mode of birth (spontaneous vaginal birth (SVB), instrumental or CS)
- Degree of perineal trauma (first, second, third and fourth degree)
- Reason for CS and decision to delivery interval for CS
- Confirmed urinary retention requiring catheterisation and pulmonary oedema
- Tachysystole (uterine contractions greater than 5 in 10 mins for 20 minutes) requiring reduction in oxytocin and/or tocolysis
- Hyperstimulation (uterine contractions greater than 5 in 10 mins for 20 minutes resulting in non-ressurring or abnormal fetal heart rate)
- Fetal blood sampling (FBS) during labour or significant STAN event (for those Units that use ST waveform analysis for intrapartum fetal monitoring)
- Abnormal cardiotocogram leading to immediate birth without fetal blood sample
- Incidence of possible maternal morbidity (anaphylaxis, pulmonary oedema, postpartum haemorrhage, shoulder dystocia, chorioamnioitis, uterine rupture/hysterectomy)
- Active management of third stage of labour
- Length of time after birth in hospital [days]
- Admission to HDU/ITU
- Maternal death

Process outcomes

- Time from randomisation to commencement of allocation
- Total oxytocin dose
- Time to maximum oxytocin rate
- Maximum oxytocin dose reached

9.3 Neonatal secondary outcomes include:

- Gender and birthweight
- Apgar score at 5 minutes

- Arterial cord blood gases when collected
- Breastfeeding rates on discharge from hospital
- Length of time after birth in hospital [days]
- Resuscitation
- Reason for neonatal review on ward (excluding routine baby check)
- Reason for admission to neonatal unit (NNU) and level of care received (level 1,2,3)including intensive care
- Duration of respiratory support
- Days to full oral feeds
- Seizures
- Neonatal encephalopathy (SARNAT grade)
- Therapeutic hypothermia (cooling) if required
- Intrapartum still birth
- Early neonatal death (within seven days of birth)

10 Safety Monitoring Procedures

The Medicines for Human Use (Clinical Trials) Regulations 2004 define categories of adverse events and it is the responsibility of investigators to notify safety events to the HOLDS Trial Office, who will forward these to the sponsor. It is the remit of the sponsor to report to the ethics committee and the MHRA. It is therefore imperative that all investigators have a thorough understanding of anticipated serious adverse events and the reporting process of these events.

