7.3 Inclusion criteria

- Nulliparous women with singleton cephalic pregnancy at term (37-42 weeks gestation)
- Confirmed delay in labour and ruptured membranes for whom the clinical decision has been made to prescribe Syntocinon for augmentation of labour

According to NICE guidance [NICE 2014], labour is established when there are regular painful contractions and progressive cervical dilation from 4 cm. Delay is suspected when cervical dilation of

< 2 cm in 4 hours occurs once labour is established. Delay is confirmed when progress of <1 cm in 2 hours is found on repeat vaginal examination.

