7.6 Obtaining informed consent

When a nulliparous woman is admitted to the labour ward potential inclusion will be checked by the midwife responsible for her care, with final eligibility determined by an obstetrician. If appropriate the trial will be discussed as her labour progresses, but raising the possibility of abnormal labour with women who are labouring normally may not be appropriate.

In line with NICE guidance once a woman is in established labour (i.e. she has regular painful contractions and her cervix is 4cms or more dilated on examination) assessment of progress includes cervical dilation as well as descent and rotation of the baby's head and changes in the strength, duration and frequency of uterine contractions. Should delay be suspected (when cervical dilation of <2cm in four hours is found) the woman remains under the care of a midwife. During the two hour period until progress is re-assessed the midwife is likely to suggest interventions which would facilitate progress occurring. She would encourage the woman to mobilise, consider hydration (e.g. a sports drink), and discuss appropriate and effective pain relief. If her membranes are still intact,

artificial rupture (amniotomy) will also be advised. It is during this two hour window that the HOLDS trial would be discussed and so the midwives role in introducing the trial and answering any questions she may have is vital.

Once delay is confirmed transfer to obstetric-led care would take place (if required) for an obstetric review and a decision about management, including the use of oxytocin. Once more the midwives' role is fundamental in ascertaining if the woman is potentially eligible, explaining the trial, answering any questions she may have and in providing continuous support.

It is acknowledged that if the woman, for whatever reason, is not able to give informed consent, recruitment is not appropriate. It may not be suitable for women in labour to be provided with lengthy information and so a summary of the trial will also be provided. After birth, information about the trial will continue to be given as and when requested.

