Confirming eligibility and obtaining consent to participate should be performed by someone with appropriate Good Clinical Practice (GCP) training and the oxytocin will be prescribed by an obstetrician. The midwives will receive appropriate and relevant training on the study protocol, and safety reporting mechanisms for the study to enable them to introduce the trial, answer any questions, randomise the woman and record dispensing of the trial Investigational Medicinal Product (IMP). She/he would then continue to manage the woman as care is not different between the two trial arms. The administration of IMP, and clinical care would normally be undertaken by such clinical midwives and therefore falls within their normal sphere of clinical practice. Therefore, the dispensing of the oxytocin can be recorded in the trial drug reconciliation chart by the midwife responsible for the woman's care and not necessarily by an obstetrician. The only difference is the strength of oxytocin and allocation is double blinded to participants, clinicians and the research team.

The qualitative work undertaken in the pilot study indicates that the recruitment processes and information provided are acceptable to women¹. Information regarding the study is given to potentially eligible women during the late antenatal period, with access to more detailed information (on the website or by request). As described previously, discussion of the trial begins when delay is suspected but consent can only be obtained once delay in labour is confirmed. The time-window for treatment to be started is relatively short as it is between diagnosis of delay and commencement of the oxytocin (which is the recommended treatment).

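### The epidural outcome has no start point, so an epidural sited before randomisation can count as an event and pull the comparison towards no difference

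*Combined protocol and SAP*

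**What the plan says.** Section 9.2 of the protocol includes "Epidural use during labour" and "Fetal blood sampling (FBS) during labour or significant STAN event" among the secondary maternal outcomes. Neither has a start point. Another item in the list does: "Time to birth from randomisation".

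Section 7.3 sets the entry condition. Delay is suspected when cervical progress of less than "2 cm in 4 hours occurs once labour is established". It then adds: "Delay is confirmed when progress of <1 cm in 2 hours is found on repeat vaginal examination". In that second interval the midwife is expected to "discuss appropriate and effective pain relief" (section 7.6), and the same section states that "consent can only be obtained once delay in labour is confirmed".

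On the analysis, section 12.2 uses all randomised women and adjusts for the minimisation variables. Section 12.2.2 treats dichotomous secondary outcomes like the primary outcome. The minimisation factors in section 8 are cervical dilation, age and maternity unit. Epidural status at entry is neither a minimisation factor nor a covariate.

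The data collection table (section 8.5) dates Labour form collection from the start of study treatment until after the birth. Section 11.1 says that data for most outcomes are transcribed from the woman's routine records.

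**The concern.** An epidural sited before randomisation cannot have been caused by the allocated dose. If it is counted, both arms gain, in expectation, the same number of events that carry no information about treatment. The risk difference shrinks, the relative risk moves towards 1 and power falls.

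A change in epidural use is a plausible maternal effect of a stronger oxytocin regimen, and section 6.3 sets out to assess maternal outcomes and safety. A diluted comparison that shows no difference could be read as reassurance, although it says less about the women who could still have had a first epidural after treatment began. About 30 units will also be transcribing the item without a stated rule on epidurals already running.

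**Working it through.** **Inputs from the plan.** Slow labour before entry: 4 + 2 = 6 hours at least (section 7.3). Target 1500 women (section 12.1), allocated 1:1 (section 8), so 750 per arm. Two-sided tests (section 12.2) at 5% (section 12.1).

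**Inputs not in the plan.** The documents give no epidural rates. The share q of women with an epidural at randomisation and the rates of new epidurals are therefore assumptions, shown over a range.

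**Power formula, checked on the plan's own figures.** With n women per arm, rates p0 and p1, and p̄ their mean:

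power = Φ{ [ |p1 − p0|·√n − 1.96·√(2p̄(1 − p̄)) ] / √(p0(1 − p0) + p1(1 − p1)) }

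Solved for n at 32% v 24% and 90% power, this gives 660 per arm, or 1320 women, exactly as in section 12.1. At 24% v 18% with 750 per arm it gives 81.5%, against the stated 80%. The same formula is used below.

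**Dilution.** Let p0 and p1 be the rates of a first epidural after randomisation in women without one at entry, with q the same in both arms in expectation.

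- Rate of any epidural in labour: q + (1 − q)·p
- Risk difference for any epidural: (1 − q)·(p1 − p0)
- Relative risk for any epidural: [q + (1 − q)·p1] / [q + (1 − q)·p0]
- At-risk analysis: rates p0 and p1, with 750·(1 − q) women per arm

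For example, at q = 0.5, p0 = 0.50 and p1 = 0.60, any epidural is 0.5 + 0.5 × 0.50 = 75% v 0.5 + 0.5 × 0.60 = 80%. The relative risk is 0.80 / 0.75 = 1.07, against 1.20 in women at risk.

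| q (assumed) | Any epidural | RR as worded | Power as worded, 750 per arm | RR at risk | Women at risk per arm | Power at risk |
|---|---|---|---|---|---|---|
| 0% | 50% v 60% | 1.20 | 97% | 1.20 | 750 | 97% |
| 10% | 55% v 64% | 1.16 | 94% | 1.20 | 675 | 96% |
| 30% | 65% v 72% | 1.11 | 83% | 1.20 | 525 | 90% |
| 50% | 75% v 80% | 1.07 | 64% | 1.20 | 375 | 79% |
| 70% | 85% v 88% | 1.04 | 40% | 1.20 | 225 | 57% |

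**Effect in the other direction.** The pattern is the same if the higher dose reduces epidural use. Assuming 40% v 32% in women at risk (RR 0.80), the relative risk as worded is 0.84, 0.90 and 0.94 at q = 10%, 30% and 50%. Power as worded v at risk is 81% v 87%, 59% v 77% and 38% v 63%.

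In every row with q above zero the at-risk analysis has more power, although it uses fewer women. At q = 0 the two analyses are the same.

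**The case against.** The strongest counter-argument is the collection window in section 8.5. Read literally, data collected only from the start of study treatment would leave out an earlier event. This has some force: a reader might infer from section 9.2 that the trial definitely counts earlier epidurals, and no passage says so. The window does not settle the matter, however. It sits in a schedule of forms and responsible staff, not in an outcome definition. An epidural sited earlier and still running when treatment starts is epidural use inside the window. Duration of the first stage, also in section 9.2, needs data from before treatment, so the window cannot bound every outcome.

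Other objections stand in part:

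- **Size.** A reader might infer that many women enter with an epidural. The documents say only that pain relief is discussed. At a 10% share little is lost.
- **Evidence of an effect.** The Cochrane review summarised in section 5.1 noted no difference in epidural analgesia, and the plan claims no power for this outcome.
- **Validity.** Any epidural in all randomised women is a legitimate intention-to-treat comparison in a trial described as pragmatic. It is diluted, not biased in its own terms. Chance imbalance in epidural status at entry is already reflected in the confidence interval, and leaving that status out of the minimisation is not an error.
- **Wording.** The contrast with the time-to-birth outcome proves little, because a time-to-event outcome must have an origin.
- **Detail elsewhere.** Section 12.2 defers detail to a separate SAP. Neither that SAP nor the case report forms are in the text supplied, so timing may already be recorded.
- **Fetal blood sampling.** A reader might extend the point in full to this outcome. The documents do not support that. Section 8.3 describes sampling during oxytocin care. Fetal distress is a contraindication in the SPC, and known SPC contraindications are exclusions (section 7.4). Nothing suggests that sampling before randomisation is common.

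**Conclusion.** The point holds for the epidural outcome as a gap in its definition. The wording allows an epidural sited before randomisation to count, and the stated analysis neither excludes nor adjusts for it. Where this happens the direction is certain: towards no difference, with the risk difference multiplied by (1 − q).

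The size is not known. For an assumed 50% v 60% in women at risk, the loss runs from 2 percentage points of power at a 10% share (94% v 96%) to 17 points at 70% (40% v 57%). These figures assume the same q in both arms, an unadjusted two-proportion comparison and complete data. They do not show that the trial would miss a real effect.

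Only a secondary outcome is affected. Caesarean section can occur only after randomisation, so the primary analysis is untouched. For fetal blood sampling and STAN events, a start point is a minor clarification.

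**What to change.** - **Data.** Record epidural in place (yes/no) on the randomisation form, and the time of siting on the Labour form.
- **Definition.** In section 9.2, define the outcome as *epidural first sited after randomisation*, analysed in women without an epidural at randomisation. This group is defined at baseline, so the randomised comparison is kept.
- **Descriptive row.** Keep any epidural in labour, in all randomised women, as a descriptive row.
- **Fetal blood sampling and STAN.** Add *after randomisation* to the wording.
- **Consistency.** Align sections 9.2, 8.5 and 12.2 and the SAP. Section 12.2 needs a stated exception to the all-randomised analysis set for this one outcome. It should also be clear that this is an outcome definition and not an addition to the subgroup analyses limited by section 12.2.4.

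The cost is one tick-box, one time transcribed from the notes and some wording. The denominator for the epidural outcome falls below 1500, and the exception has to be explained in the report. If status and time are not captured prospectively, they would have to be recovered from records at about 30 units.

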10.1 General Definitions

10.1.1 Adverse Reactions (ARs)

An AR is an adverse event that is considered to have a "reasonable causal relationship" with any trial drug.

10.1.2 Adverse Events (AEs)

An AE is any unintentional, unfavourable clinical sign or symptom.

The following are not AEs and do not require reporting:

- A pre-existing condition (unless it worsens significantly during treatment).
- Diagnostic and therapeutic procedures, such as Caesarean section

10.1.3 Serious Adverse Reactions (SARs) or Serious Adverse Events (SAEs)

Any AR or AE that at any dose:

- Results in death
- Immediately threatens the life of participant*
- Results in hospitalisation or a longer than anticipated stay in hospital
- Results in a persistent or significant disability or incapacity

*Life-threatening in the definition of a serious adverse event refers to an event in which the mother was at risk of death at the time of the event. It does not refer to an event which hypothetically might have caused death if it were more severe. Important adverse events that are not immediately life-threatening or do not result in death or hospitalisation, but may jeopardise the pregnancy or may require intervention to prevent one of the other outcomes listed in the definition above, should also be considered serious.

The definition of a SAR or SAE usually includes any congenital anomaly or birth defect in any pregnancy; however, the intervention is given briefly towards the end of labour beyond 37 weeks' gestation where it cannot have any possible teratogenic effect. Any babies with congenital anomalies will not be considered to be a SAR or SAE

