10.5 Reporting SARs/SAEs

All maternal or neonatal SARs/SAEs, from the commencement of the trial treatment until discharge from hospital, must be recorded on the SAE form and faxed to BCTU on [name] within 24 hours of the research staff becoming aware of the event. Alternatively, the report can be emailed as a PDF attachment to the HOLDS email address from a NHS email account. The Principal Investigator (or other nominated obstetrician) is required to assign seriousness, causality and expectedness to the SARs/SAEs before reporting. All SARs/SAEs should be assessed for seriousness, causality and expectedness.

For each SARs/SAEs, the following information will be collected:

- full details in medical terms with a diagnosis, if possible
- its duration (start and end dates; times, if applicable)
- action taken
- outcome
- causality, in the opinion of the investigator*
- whether the event would be considered expected or unexpected* (refer to Reference Safety Information)

*Assessment of causality and expectedness must be made by an obstetrician. If an obstetrician is unavailable, initial reports without causality and expectedness assessment should be submitted to Trial Office by a healthcare professional (i.e., HOLDS midwife) within 24 hours, but must be followed up by medical assessment as soon as possible thereafter, ideally within the following 24 hours.

The local Principle Investigator and others responsible for the woman's or baby's care should institute any supplementary investigations of SARs/SAEs based on their clinical judgement of the likely causative factors and provide further follow-up information as soon as available.

SARs/SAEs still present beyond 28 days post-partum must be followed up until the final outcome is determined.

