10.6 Reporting SUSARs

SAEs categorised by the local investigator as **both** suspected to be related to the trial drug **and** unexpected are SUSARs, and are subject to expedited reporting. All SUSARs must be recorded on the SAE Form and faxed to the BCTU on [name]. Alternatively, the report can be emailed as a PDF attachment to the HOLDS email address from a NHS email account, within 24 hours of the research staff becoming aware of the event. The Chief Investigator (CI) or nominated individual will undertake urgent review of SUSARs within 24 hours of reporting and may request further information immediately from the patient's clinical team. The CI will not overrule the causality, expectedness or seriousness assessment given by the local investigator. If the CI disagrees with the local investigator's assessment, further clarification and discussion should take place to reach a consensus. If a consensus cannot be reached, both the opinion of the local investigator and the CI should be provided in the report to the MHRA and the REC.

The BCTU will report all SUSARs to the MHRA and the main REC. If the SUSAR resulted in death or was life-threatening this will be done within 7 days of the initial report being received or within 15 days for any other SUSAR. If information is incomplete at the time of initial reporting, or the event is ongoing, the BCTU will request follow-up information, including information for categorisation of causality, from the local investigator and will send the follow-up information to the MHRA and main REC within an additional 8 days for fatal or life-threatening SUSARs and as soon as possible for any other events.

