10.7 Safety reporting responsibilities

10.7.1 Local Principal Investigator (or nominated individual in PI's absence)

- To record all safety events that occur in the women taking part in the trial. This includes serious, expected or unexpected adverse events, unless defined as outcomes above
- Medical judgement in assigning expectedness and causality to SAEs
- To fax SAE forms to BCTU within 24 hours of becoming aware, and to provide further followup information as soon as available
- To report SARs/SAEs to local committees if required, in line with local arrangements
- To sign an Investigator's Agreement accepting these responsibilities

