11.3 Definition of the End of Trial

The trial will be deemed complete when the last recruited woman has given birth and outcome data collected and entered onto the data collection system.

For participants the End of Trial is end of discharge from maternity unit or death for the mother and discharge from maternity or neonatal unit or death with 7 days for the baby.

12 Statistical methods and analysis

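### Life-threatening is defined by risk to the mother only, so read literally a non-fatal SUSAR that threatens only the baby's life falls on the 15-day reporting clock instead of the 7-day one

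*Combined protocol and SAP*

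**What the plan says.** Among the seriousness criteria in section 10.1.3 is an event that "Immediately threatens the life of participant". An asterisk leads to a footnote under which the term "refers to an event in which the mother was at risk of death at the time of the event". The footnote does not mention the fetus or the newborn, and no other section defines the term.

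Section 10.6 sets the time limits for sending SUSARs to the regulator and the ethics committee. The fast limit reads: "If the SUSAR resulted in death or was life-threatening this will be done within 7 days of the initial report being received". All remaining SUSARs have a limit of 15 days. Outstanding information then follows "within an additional 8 days for fatal or life-threatening SUSARs and as soon as possible for any other events".

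Other sections bring the baby into scope:

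- Section 10.5 sets the reporting duty for "All maternal or neonatal SARs/SAEs, from the commencement of the trial treatment until discharge from hospital".
- Section 10.4 lists six neonatal events to be reported as SAEs: unexpected intensive care, seizures, encephalopathy, therapeutic hypothermia, intrapartum stillbirth and neonatal death.
- Section 11.3, in defining the end of trial for participants, includes "discharge from maternity or neonatal unit or death with 7 days for the baby".

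Section 10.7.1 points the other way. It asks the local investigator to record "safety events that occur in the women taking part in the trial" and does not mention babies.

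**The concern.** The trial has two patients per randomisation, and the safety sections cover both until they reach the word that controls the fastest external report. There the text narrows to the mother. An investigator or trials-unit officer who follows the footnote would not class an event as life-threatening if the mother was well and only the baby was in danger.

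What is at stake is the time limit for notifying the regulator and the ethics committee. The other external routes for a non-fatal event are slower or discretionary. Under 10.5, SARs and SAEs go to the MHRA and REC annually, and to the DMC on an agreed timetable. Under 10.7.3 only fatal SAEs go to the DMC for continuous review. Under 10.7.2 the Chief Investigator alerts the DMC Chair if concerned. Neonatal safety is a stated objective in 6.3, so the limit for the baby should not depend on how a reader resolves an inconsistent footnote.

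**Working it through.** No statistical calculation applies. The check is to apply the written rules to each kind of SUSAR.

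**Step 1: which clock applies.** Inputs are the footnote in 10.1.3 and the limits in 10.6.

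| SUSAR | Fatal? | Life-threatening as defined? | First report | Follow-up information |
|---|---|---|---|---|
| Mother dies | yes | – | 7 days | 8 further days |
| Mother survives, her life was at risk | no | yes | 7 days | 8 further days |
| Baby dies | yes | – | 7 days | 8 further days |
| Baby survives, only the baby's life was at risk | no | no | 15 days | no fixed limit |

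The third row keeps the fast clock because the reference to death in 10.6 is not confined to the mother. Only the fourth row changes.

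**Step 2: size of the difference.** First report: 15 − 7 = 8 days. For follow-up, if the additional 8 days run from the end of the 7-day period, the maternal case is due in full by 7 + 8 = 15 days. For the baby, the first report may be due only on day 15, with no fixed limit after it.

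**Step 3: is the fourth-row event still serious?** Generally yes. Section 10.1.3 also counts a hospital stay longer than anticipated, lasting disability, and important events that need intervention to prevent a listed outcome. Death is a listed outcome, so a newborn collapse that needed full resuscitation would qualify even without intensive care. The list in 10.4 is also expressly not exhaustive. Being serious by one of these routes does not restore the 7-day clock, which depends on death or on the defined term.

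**Step 4: how many events can be affected?** The event must be suspected to be related and also unexpected (10.6). Expectedness is judged against the SPC (10.1.4, 10.2). The SPC table for the fetus and neonate (section 4.8, Appendices One and Two) lists foetal distress, asphyxia and death, and neonatal hyponatraemia. Those are expected unless their severity takes them beyond the listing. Neonatal encephalopathy and neonatal seizures are not named in that table. Seizures do appear in the SPC text as a symptom of water intoxication, so encephalopathy is the clearer example. Section 10.4 also describes its listed events as having no causal association with the drug, which could keep some of them from being classed as SUSARs at all. The affected set is therefore small but not shown to be empty. The documents give no rate from which to estimate a count.

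**The case against.** The strongest reply is that the footnote limits itself to the term as used in defining an SAE, and 10.6 does not refer back to it. The criterion it annotates says participant, and if 11.3 makes the baby a participant, the criterion already covers the baby. On that view the text is ambiguous and does not set a mother-only rule. This stands in part: carrying the footnote into 10.6 is an inference. But the footnote is the only definition supplied, and if it is set aside, the clock for a baby who survives has no definition at all. Either way the passages need reconciling.

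The second reply is that little is delayed in practice. Every maternal or neonatal SAR or SAE goes to BCTU within 24 hours of staff becoming aware of it (10.5), and the Chief Investigator reviews each SUSAR within 24 hours of reporting (10.6). Neonatal co-applicants share in the assessment of causality and expectedness (10.5, 10.7.2). This stands. Only the outer limit for external notification differs.

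Third, the phrase in 10.7.1 is a summary line, and the operative rule in 10.5 covers both patients. This also stands. The 10.7.1 wording is a point of consistency, not a separate gap.

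A reader might go further and infer that a life-threatening neonatal event could escape being reported as serious. The documents do not support that, because the other criteria in 10.1.3 and the open list in 10.4 would catch it. A reader might also infer that the main harms the SPC warns of, foetal distress and asphyxia, are put on the slow clock. They are listed reactions, so they would normally not be SUSARs and would get neither clock. Correcting the footnote would not change that.

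**Conclusion.** The point holds for one class of event: a non-fatal SUSAR that threatens the baby's life and not the mother's. As written, its outer limit for reporting to the MHRA and main REC is 15 days instead of 7, and the 8-day follow-up limit does not apply. The conclusion assumes that the 10.1.3 footnote supplies the meaning of life-threatening in 10.6, which is the only reading the text offers.

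The class is narrow: neonatal reactions not listed in the SPC, or listed ones of unexpected severity, in babies who survive. Reporting to the trials unit, review by the Chief Investigator, and the clock for fatal neonatal SUSARs are unaffected. No estimate, test or sample size depends on it. The severity is minor to moderate. It is worth correcting because it is an internal contradiction in an expedited-reporting rule and the correction costs little.

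**What to change.** Reconcile the passages with three wording changes:

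- **10.1.3 footnote:** replace *the mother* with *the mother or the baby (fetus or neonate)*. Both terms are needed because the reporting period begins when trial treatment starts, before birth.
- **10.6:** state that the 7-day limit and the 8-day follow-up limit apply to fatal or life-threatening SUSARs in either the mother or the baby.
- **10.7.1:** refer to women and babies, to match 10.5.

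The SAE form should let the reporter mark whose life was at risk. Treatment, design, sample size and analysis do not change. The cost is a protocol amendment, one form field and possibly a few extra 7-day reports.
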